### 2.1. AIM

This study aims to develop and validate two clinical prediction models to estimate the risk of a patient developing AF in the seven days following cardiac surgery, using data available:

- In the pre-operative assessment clinic or at admission for surgery (PARADISE-1)
- On arrival to the post-operative care unit (PARADISE-2)

### 2.2. OBJECTIVES

To develop and internally validate two prognostic models to predict postoperative atrial fibrillation after cardiac surgery using data available in the pre-operative assessment clinic or at admission for surgery (PARADISE-1); and data available on arrival in the postoperative care unit (PARADISE-2) from a single US centre (Massachusetts General Hospital).

To externally validate the developed models on three separate datasets: a US hospital (Brigham and Women's Hospital), a UK clinical trial (Tight K study) and prospectively collected data from UK NHS cardiac surgery centres.

### 3. METHODOLOGY

This is an international, multi-centre longitudinal cohort study of patients who have undergone cardiac surgery. The study will use retrospective data to develop clinical prediction models to estimate the risk of developing atrial fibrillation in the seven days following surgery and use prospectively collected data to externally validate the developed models.

### 3.1. STUDY POPULATION

#### 3.1.1. INCLUSION CRITERIA

- Patients 18 years or over
- Who underwent or are scheduled to undergo cardiac surgery

#### 3.1.2. EXCLUSION CRITERIA

- Patients who have requested that their data not be used for research
- Patients with paced rhythm
- The procedure was solely:
  - A transcatheter insertion of a valve or stent
  - An Isolated vascular procedure (aorta, pulmonary artery)
  - o A heart transplant
  - A lung transplant
  - For congenital heart disease

#### 3.2. OUTCOME MEASURE

A new onset atrial fibrillation was defined as present if current atrial fibrillation or flutter was mentioned in patient cardiac report (e.g., ECG, ECHO) OR atrial fibrillation was identified by a trained chart abstractor for The Society of Thoracic Surgeons Adult Cardiac Surgery Database during postoperative period during the hospital admission (the outcome was assumed to happen within 7 days when timing was not specified).

Prior AF status was defined as any previous history of AF. Models for prior AF patients will be investigated in the sub analysis (section 3.6)

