2 LAY SUMMARY

Atrial Fibrillation (AF) is a common abnormal heart rhythm. AF causes the heart to beat irregularly and sometimes very rapidly. About 30-50% of patients develop AF after heart surgery. These patients stay longer on the Intensive Care Unit (ICU) after surgery, are more likely to develop complications and have a higher risk of dying. Avoiding AF is important.

Some drugs, including beta blockers and amiodarone may help prevent AF if given after surgery. However, these may also lead to complications (such as lung damage). It is therefore important to identify which patients are most likely to benefit from these treatments (i.e., where the benefits outweigh the risks). There are existing tools designed to predict the risk of suffering AF after heart surgery. However, they are unreliable and therefore not used in clinical practice. A modern, reliable risk prediction tool is needed.

The PARADISE study will develop and test new prediction tools to identify which patients are most at risk of developing AF after heart surgery. We will focus our tools on those patients who most commonly develop AF, such as those who have had surgery to repair a valve or blood vessel in their heart.

To do this we will:

- Review the medical literature and assemble a panel of medical experts to create a list of known factors that affect patients' risk of AF after heart surgery
- Use a large UK general practice database (CALIBER) to see whether we can find new risk factors.
- Ask the expert panel to agree a list of known and new risks factors to be included in the prediction tool.
- Develop two new prediction tools using an existing American cardiac surgery database (the Partners research Database). The first will be used before surgery, the second immediately following surgery. Two models are needed as events during surgery may alter the risk of AF.
- Test how reliably our new tools predict which patients suffer AF after surgery, with data from large UK NHS heart centres, one US Hospital (Brigham) and a UK clinical trial (Tight-K).
- We will work with two charities (AF Alliance and StopAfib) to share our results with patients and the wider public.

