12.3 Data Recording and Record Keeping

All study records will be electronic – an overview of their generation is detailed above. All records will be subject to quality assurance polices both at the University and research group level. These are designed to guarantee the accuracy and validity of the study data.

The participants will be identified by a unique study number (pseudonymous study key).

We will use the CALIBER and PRD data sources to validate known (and potentially identify novel) risk factors for AF after cardiac surgery. A complete list of risk factors will not be known a priori, as it depends on the results of the systematic review and Delphi process. However, likely required data will be contained within following categories:

- Demographics (e.g., age, sex, ethnicity)
- Diagnostic coding (e.g., known chronic conditions)
- Limited pre- and post-operative medications (e.g., beta-blockers, vasoactive drugs)
- Limited surgical procedures and intraoperative findings (e.g., type of cardiac surgery, duration of bypass, blood transfusion)
- laboratory blood tests (including blood gases)
- vital signs (e.g., heart rate, blood pressure)
- Limited Echocardiogram findings
- Limited electrocardiogram (ECG) findings

Excluding age, sex and ethnicity we will not be accessing data on protected characteristics (e.g., religion, civil status, sexual orientation).

The expert panel will agree a final list of risk factors, which will be used to develop the two prediction models.

The models will be validated in one US data set (Brigham), one clinical trial data set (Tight-K) and prospective data collected from UK cardiac surgery centres (NHS Trusts). Only data from the above categories included in the candidate risk factor list agreed by the expert panel will be extracted from the UK cardiac centres along with the required outcome data for model assessment (including in-hospital

CONFIDENTIAL

mortality and episodes of atrial fibrillation). Tight-K is an ongoing clinical trial with its own approvals. Data for the NHS Trust data sets will be acquired from the individual Trusts patient records in collaboration with the respective organisations.

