#### 3.6. SUB ANALYSIS

An additional analysis will be investigated to include patients with prior AF. Models (both regression model and machine learning approaches) will be developed to population include prior AF patient (compared to population for patients exclude prior AF). Model coefficients and performance will be compared between patients with and without prior AF.

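### Flutter counts as an outcome event in cardiac reports, but is not named in the registry limb or in the prior-AF definition, so recurrent flutter can be scored as new-onset AF

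*SAP*

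**What the plan says.** SAP 3.2 builds the development outcome from two limbs joined by OR. In the first, the outcome is "defined as present if current atrial fibrillation or flutter was mentioned in patient cardiac report", with ECG and echo given as examples of such reports. The second is met when "atrial fibrillation was identified by a trained chart abstractor for The Society of Thoracic Surgeons Adult Cardiac Surgery Database". The next paragraph of the same section sets prior status: "Prior AF status was defined as any previous history of AF". Flutter is named in the first limb only, and nowhere else in the SAP or the protocol. The protocol's lay summary expands the abbreviation as fibrillation: "Atrial Fibrillation (AF) is a common abnormal heart rhythm".

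Patients with prior AF are not listed among the exclusions in SAP 3.1.2. SAP 3.2 and 3.6 nevertheless treat them as outside the main model: "An additional analysis will be investigated to include patients with prior AF". SAP 3.3.1 states that both Massachusetts General sources, the hospital record registry and the STS database, are used for development.

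For the UK centres, Protocol 12.3 says that the outcome data to be extracted include in-hospital mortality and "episodes of atrial fibrillation". For Tight K, SAP 3.8.1 refers to that trial's own AFACS definitions and says nothing about flutter.

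**The concern.** A new-onset outcome needs the event and the prior-history rule to cover the same rhythms. Here the event covers two in one limb, while the history covers one. A patient with known flutter can therefore enter the new-onset cohort, and a return of that same rhythm is then learned by the model as a new event. This works against the separation of prior from new arrhythmia that the SAP sets up.

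There are two secondary consequences. First, within development, flutter recorded in a chart but in no cardiac report is not an event under the wording, so the label for one rhythm depends on which record exists. Second, the treatment of flutter in the Brigham, NHS Trust and Tight K data is not stated. The protocol (synopsis and section 6) names the calibration intercept and slope in external data as primary, alongside the c-statistic. Protocol 11.2.2 and the external validation section of the SAP plan to look at recalibration on the ground of case-mix. If development counted flutter and a validation set did not, part of the intercept would reflect the definition, and it could be recalibrated away as though it were a population difference.

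**Working it through.** **1. The rules applied to individual patients (literal reading of SAP 3.2)**

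| Patient | Prior AF? | Outcome label in the main cohort |
|---|---|---|
| Past flutter, no past AF; flutter on postoperative ECG or echo report | No | New-onset AF event (a recurrence) |
| Past flutter, no past AF; first fibrillation after surgery | No | New-onset AF event (correct for AF) |
| No past arrhythmia; flutter on postoperative ECG or echo report | No | Event |
| No past arrhythmia; flutter noted only in the abstracted chart | No | Not an event as worded |
| Past AF | Yes | Outside the main model (SAP 3.6) |

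Row 1 is the mislabelled group. Rows 3 and 4 differ only in the record that holds the rhythm. Because the limbs are joined by OR, flutter in any cardiac report counts whatever the registry says, so row 4 is confined to flutter that reached no cardiac report.

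**2. The plan's own figures that depend on prevalence**

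Inputs: p = 0.20 and about 12,000 surgeries (SAP 3.3.2), which gives 12,000 × 0.20 = 2,400 events; O/E interval width 0.2 (SAP 3.8.2), which corresponds to SE(ln O/E) = 0.051.

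- O/E criterion: n = (1 − p)/(p × SE²) = 0.8/(0.2 × 0.051²) = 1,537.9, so 1,538 patients and 308 events. This matches SAP 3.8.2.
- Predictor parameters: n(S − 1)ln(1 − R²/S), with S = 0.9 (assumed) and R² = 0.0316 or 0.0948, gives 42 and 133 against the stated 42 and 132.

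These figures reproduce. The point does not dispute them.

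**3. What a definition mismatch alone could do (illustration)**

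The documents give no flutter rate. Assume that a share f of development events is flutter only, and that a validation set with the same true risk leaves those events out. Its prevalence is then 0.20(1 − f), O/E is 1 − f, and the approximate intercept shift is logit[0.20(1 − f)] − logit(0.20), where logit(0.20) = ln(0.20/0.80) = −1.386.

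| Assumed f | Events affected (2,400 × f) | Prevalence | O/E | Approximate intercept shift | n for O/E criterion |
|---|---|---|---|---|---|
| 2% | 48 | 19.6% | 0.98 | −0.03 | 1,578 |
| 5% | 120 | 19.0% | 0.95 | −0.06 | 1,640 |
| 10% | 240 | 18.0% | 0.90 | −0.13 | 1,752 |
| 15% | 360 | 17.0% | 0.85 | −0.20 | 1,878 |

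Worked line for 5%: ln(0.19/0.81) = −1.450, and −1.450 − (−1.386) = −0.06.

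The O/E requirement stays below the 4,248 that SAP 3.8.2 sets as its overall minimum (the slope criterion behind 4,248 was not recalculated). The number of predictor parameters allowed barely moves: 40 to 126 even at 15%.

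**4. Net direction**

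SAP 3.3.2 gives about 20% new-onset AF in development. SAP 3.8.1 gives about 2,000 events in 6,000 NHS patients, that is 2,000/6,000 = 33%. Without any flutter question, these rates point to observed risk above predicted risk in the UK. A flutter mismatch of the kind in step 3 would pull the other way by an unknown amount.

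**The case against.** The strongest reply is that this is shorthand. SAP 3.2 itself uses new-onset atrial fibrillation as the name of an outcome that includes flutter, so AF in the prior-status sentence may carry the same meaning. The registry's data dictionary might count flutter under its AF item, and Case Report Form v2.1, which SAP 3.3.3 cites for the candidate predictors, might define prior AF more widely. Neither can be seen here. This is a fair limit: the mislabelling follows from the words as written and is not a declared intention. It does not remove the need for a change, because two analysts working from SAP 3.2 could build different labels.

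Several stronger readings are tempting, and the documents do not support them:

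- A reader might infer that the UK data leave flutter out. Protocol 12.3 gives its outcome list as what is included, in a data-management section. It is silent on flutter and does not exclude it.
- A reader might infer that the model will over-predict in the UK. The documents' own rates, about 20% against about 33%, point the other way before flutter is considered.
- A reader might treat O/E as a primary outcome. It appears only as a sample-size criterion in SAP 3.8.2; the primary calibration measures are the intercept and slope.
- A reader might count every postoperative event in patients with past flutter as mislabelled. A first fibrillation in such a patient is genuinely new-onset AF; only returning flutter is at issue.
- A reader might think that the registry limb loses flutter widely. The OR join limits the loss to flutter in no cardiac report.

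It can also be said that the planned recalibration would absorb a roughly constant shift. That would limit the effect on an updated UK model, but would not show that the cause was a definition. Nor would it correct the labels in the development data.

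**Conclusion.** The point holds as an inconsistency of definition in SAP 3.2. The outcome admits flutter through one limb, while the prior-status rule names AF only, so as written a patient with past flutter and no past AF is scored as new-onset AF when flutter recurs on a postoperative cardiac report. Two gaps go with it: flutter outside the cardiac reports is not an event, and the handling of flutter in the validation sets is not stated.

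The number of patients affected, and the net direction of any effect on UK calibration, cannot be given from the documents. The 2% to 15% range above is an assumption, and its intercept shifts of about −0.03 to −0.20 arise only if a validation set does omit flutter. The sample-size figures checked here are not undermined. This should be settled before the outcome and cohort variables are derived, but it does not threaten the design.

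**What to change.** In SAP 3.2, define prior status as any previous history of atrial fibrillation or atrial flutter, so that it matches the outcome. State the outcome as atrial fibrillation or atrial flutter in both development limbs, and apply the same composite in the Brigham, NHS Trust and Tight K data wherever flutter is recorded. In SAP 3.8, say for each validation set whether flutter is available. Where a source, whether the STS limb or a validation set, records AF only, add an analysis with an AF-only outcome in both development and validation so that the two sides match; fibrillation and flutter in cardiac reports then need to be coded separately.

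The cost is SAP wording, a code-list change and possibly one extra refit. A few patients move from the new-onset group to the prior group, and event counts in the main model fall slightly as a result. If the STS data do not hold flutter separately, that limb cannot be widened after the fact; the SAP should say so and rely on the AF-only analysis as the check.

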This study will develop and validate two different scores as they apply to different situations, in the preoperative assessment clinic (PARADISE 1) and on arrival in the post-operative care unit (PARADISE 2), have different input variables (the latter including intra-operative and immediately available postoperative variables) and different time horizons for prediction (from weeks before the operation and from immediately post-operative in the post-operative care unit). These two models will have two distinct use cases. For example, PARADISE-1 could be used to start prophylactic medication in the preoperative assessment clinic, whereas PARADISE 2 will be used to adjust risk on admission to the postoperative care unit. Of the patients who develop AFACS, 70% do so before post-operative day 4 and 94% by post-operative day 7 [6, 27]. Therefore, both models will be optimised to predict AFACS within the first week of the initial post-operative hospital stay. This ensures we address the unmet need for prediction of AF following cardiac surgery, rather than AF in the context of prolonged hospitalisation or critical illness.

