#### 3.3.2. SAMPLE SIZE CALCULATION

As the two models to be developed are predicting the same outcome (new onset AF in the 7 days after surgery), the same sample size is applicable to both models.

Data on approximately 12,000 surgeries are available from Massachusetts General Hospital between 2003 – 2020 with approximately 20% of patients having new onset AF in the 7 days after surgery.

We used formal sample size formulae for binary outcome measurement provided by Riley et al [28] and the associated 'pmsampsize'[29] sample size calculator in R statistical software programme to calculate the maximum number of candidate predictor parameters we can include during model development. Based on the prevalence and assuming an anticipated R squared between 5% and 15% of the max Cox-Snell R2 (i.e. Cox-Snell R2 between 0.0316 and 0.0948) we can examine up to 42 - 132 predictor parameters for inclusion in the model [28].

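### SAP 3.2 counts every undated in-hospital AF as a 7-day event; in stays longer than 7 days this can admit late AF, by an amount the plan neither reports nor tests

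*SAP*

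**What the plan says.** SAP 2.1 sets the target: to "estimate the risk of a patient developing AF in the seven days following cardiac surgery". SAP 3.3.2 uses the same 7-day outcome for the sample size. SAP section 2 (and Protocol 5.1) explains the choice of horizon: "Of the patients who develop AFACS, 70% do so before post-operative day 4 and 94% by post-operative day 7". The intention is to predict AF that follows surgery, "rather than AF in the context of prolonged hospitalisation or critical illness".

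SAP 3.2 defines the outcome from two sources: a mention of current AF or flutter in a cardiac report, or AF identified by a trained chart abstractor for the surgical registry. The period given is "during postoperative period during the hospital admission", with no day-7 limit written in. For events without a date, "the outcome was assumed to happen within 7 days when timing was not specified".

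Neither document says how many events lack a date, which source they come from, or whether the same default applies in the validation sets. The closest planned check is in SAP 3.4.1: an optional analysis of informative missingness, which does not mention the timing of AF.

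**The concern.** The rule can err in one direction only. An undated in-hospital event in a stay of 7 days or less must lie inside the window. In a longer stay, an undated event may have begun after day 7 and still be labelled a 7-day event. A true 7-day event is never lost this way. Any error is therefore confined to patients with long stays, the group whose late AF the plan says it is not trying to predict.

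Two things are at stake. First, calibration in external data is part of the primary outcome (Protocol section 6). Late events counted in development raise the predicted risk relative to data in which events are correctly dated. Secondly, because the mislabelling is tied to long stay, predictors of a complicated course could gain some weight. That direction is plausible, but nothing in the documents lets it be quantified.

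**Working it through.** **Inputs.** About 12,000 development surgeries and 20% with 7-day AF (SAP 3.3.2). An alternative incidence of 18% (SAP 3.3.4). 94% of AFACS by day 7, so 6% later (SAP section 2). The undated share *u* is not in the documents, so a range of 10% to 100% is assumed.

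**The plan's own figure first.** SAP 3.3.2 gives a limit of 42 to 132 candidate parameters. The shrinkage criterion is P = −n(1 − S) ln(1 − R²/S). With n = 12,000, Cox-Snell R² of 0.0316 and 0.0948, and S = 0.9 (assumed; the SAP does not state it), P is 42.9 and 133.6. The stated limit is reproduced to within 3%.

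**Events mislabelled.** Events = 12,000 × 0.20 = 2,400. If missing dates are unrelated to onset day, the late events counted as 7-day events number 2,400 × 0.06 × *u*, and O/E in correctly dated data is multiplied by 1 − 0.06*u*:

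| Undated share | Mislabelled events | Share of events | O/E multiplier |
|---|---|---|---|
| 10% | 14 | 0.6% | 0.994 |
| 25% | 36 | 1.5% | 0.985 |
| 50% | 72 | 3.0% | 0.97 |
| 100% | 144 | 6.0% | 0.94 |

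This treats 2,400 as the count before any dated late AF is removed. If it is the count after removal, the contaminated share is 0.06*u*/(0.94 + 0.06*u*), which gives 15, 38, 74 and 144 events. The difference is immaterial.

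**Ceiling.** The largest effect arises when all late AF is undated: 144 events, which is 144/12,000 = 1.2% of surgeries. True 7-day events would be 2,400 − 144 = 2,256, or 18.8%. The intercept would differ by logit(0.20) − logit(0.188) = 0.077. At 18% incidence the ceiling is 2,160 × 0.06 ≈ 130, leaving about 2,030 events (16.9%).

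**If late AF is more often undated.** With 25% undated (600 events) and all late AF among them, 144/600 = 24% of the undated events would be late. The total still cannot exceed the ceiling.

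**Effect on sample size.** At 18.8% prevalence the parameter limit is about 42 to 130, so it hardly moves.

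**Set against expected incidence.** The plan expects about 2,000/6,000 = 33% in the NHS cohort (SAP 3.8.1) and about 900/3,000 = 30% in Brigham (Protocol 7.5). Before any case-mix adjustment, and against a 20% development incidence, crude O/E is 0.30/0.20 = 1.50 to 0.333/0.20 = 1.67. With the ceiling removed from development, it would be 0.30/0.188 = 1.60 to 0.333/0.188 = 1.77. On these figures the rule changes the size of an expected under-prediction and does not reverse it.

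**The case against.** The assumption is openly declared and is a reasonable default if 94% of AFACS starts by day 7. That 94% is a cited background figure, not a measurement at the development centre. The largest numbers need all late AF to be undated. The mislabelled share of surgeries is small (1.2% at most, 0.3% at 25% undated). The SAP's own precision target for O/E is a confidence interval of width 0.2, roughly 0.9 to 1.1, and even 0.94 lies inside it. All of this stands, and it limits the size of the point.

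A reader might go further and infer that the models will over-predict in validation, and that this will be mistaken for a US/UK case-mix difference. The documents do not support that:

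- The expected incidences point to crude under-prediction.
- The documents do not say how validation events are dated, so the contrast between undated development events and dated validation events is itself an assumption.
- Brigham is also a US set, so a dating artefact confined to the development hospital could appear there too.
- Recalibration for the UK is to be investigated in any case.

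A reader might also note that, with 6,000 patients at 20% incidence, the standard error of ln(O/E) is √(0.8/1,200) = 0.026, which puts 0.94 at 2.4 standard errors from 1. That is the ceiling only. At 50% and 25% undated the distances are about 1.2 and 0.6.

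Finally, both documents link AFACS to longer hospital stays. Many undated events in long stays may therefore be early AF, and counting none of them could misclassify more events than the present rule does. This argues against simply discarding them. It does not argue against testing the rule.

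**Conclusion.** The point holds in a limited form. The default in SAP 3.2 conflicts with the 7-day target for undated AF in stays longer than 7 days. Its error runs only from late to early, and no check on it is committed to.

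If the cited 94% applies at the development centre, at most 6% of events are affected: 144 of 2,400 at 20% incidence, or about 130 of 2,160 at 18%. The number is smaller in proportion if only some dates are missing and missingness is unrelated to onset day. The rule multiplies O/E in correctly dated data by about 0.94 to 1.0. Net over-prediction is not established, the effect on individual predictors is unquantified, and the development sample size is essentially untouched.

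What the plan lacks is the one figure that would settle whether this matters: the number of undated events, and how many of them fall in stays longer than 7 days.

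**What to change.** Amend SAP 3.2 as follows:

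1. Date abstractor-flagged events from the hospital-record (RPDR) cardiac reports where one exists, and state that AF dated after day 7 is not an event.
2. Accept an undated event as a 7-day event without further check only when the postoperative stay was 7 days or less.
3. For undated events in longer stays, the current assumption may remain the primary rule. Commit, though, to a sensitivity analysis that refits the models and re-reports calibration and discrimination twice: once with these events counted as non-events, and once with their 7-day status multiply imputed. The imputation planned in SAP 3.4.1 already includes the outcome; length of stay would be a natural auxiliary variable. The non-event version is a bound, not a better estimate. The imputed version assumes that dated events represent undated ones.
4. Report the number of undated events by source and by record-system era (before and after the April 2016 change), and state whether the same rule applies in each validation set.

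The cost is SAP wording and some analysis work. The stated incidence may fall slightly. No new data are needed if discharge dates are held, which is likely for hospital records but is not stated.
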